7.2.1. Dose Levels

Dose levels to be explored are shown in [Table 4](#).

Table 4: Dose Levels

Dose Level	CC-122 Dose (mg)	CC-122 Schedule (days)	Nivolumab Dose (mg/kg)	Nivolumab Schedule
- 1	1.0	5/7	3.0	Every 2 weeks
1	2.0	5/7	3.0	Every 2 weeks
2	3.0	5/7	3.0	Every 2 weeks
3	4.0	5/7	3.0	Every 2 weeks

Dosing will start at dose level 1. Each dose level must be cleared by the SRC based on review of all available clinical, safety, PK, PD and laboratory data before initiating the next higher dose level. The study intends to identify the RP2D at or below the 4.0 mg dose level, however intermediate or higher dose levels may be explored at the discretion of the SRC.

During dose escalation, the decision to either evaluate a higher dose level, an intermittent dose schedule, or declare the RP2D (or if applicable NTD) will be determined by the SRC, based on their review of all available clinical data, PK, PD and laboratory safety data for a given dose cohort.

Intra-subject dose escalation of CC-122 is not permitted during Cycle 1, but may be permitted in later cycles if approved by the SRC.

Dose reduction of CC-122 and temporary interruption of one or both IPs due to toxicity during Cycle 1 is allowed but may constitute a DLT, as outlined in Section 7.6 and 7.9.

Study treatment may be discontinued if there is evidence of clinically significant disease progression, unacceptable toxicity or subject/physician decision to withdraw. Subjects may continue to receive CC-122 and nivolumab beyond disease progression at the discretion of the Investigator.

If any subject continues to experience unacceptable toxicity after permitted IP adjustments, one or both IPs will be discontinued permanently.

The estimated total number of subjects to be enrolled during dose escalation is approximately 20 to 30, depending on cohort size. Up to 30 additional subjects will be evaluated for safety, PK, PD, and preliminary anti-tumor effects in one or two expansion cohorts.

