Events meeting the DLT definition occurring beyond the first cycle will be taken into account when determining the RP2D. Any AE with the potential to become a DLT based on the duration should be followed appropriately to accurately determine the duration of the event.

Subjects should delay/interrupt or discontinue treatment if they experience any adverse event, laboratory abnormality or intercurrent illness (regardless of causality) which, in the opinion of the investigator, presents a substantial clinical risk to the subject with continued dosing of any IP. Such delay/interruption or discontinuation, however, will not be considered a DLT unless it meets at least one of the DLT criteria defined above or if deemed dose-limiting by the SRC.

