7.8. Criteria for Dose Escalation

The SRC will make dose escalation decisions. The decision criteria for dose escalation are:

- If no DLT is observed in the first 3 evaluable subjects during the first cycle, dose escalation to the next higher dose level may occur.
- If 1 out of 6 evaluable subjects experiences DLT during the first cycle, dose escalation to the next higher dose level may occur. Additional subjects will be enrolled to expand the cohort to 6 evaluable subjects if less than 6 subjects are evaluable when the DLT is observed.
- If 2 or more out of up to 6 evaluable subjects experience a DLT during the DLT assessment period in a cohort, any further recruitment into that cohort will cease and this dose will be defined as an NTD.
- The SRC will determine if additional subjects will be enrolled in a parallel or at lower dose cohorts to have 6 evaluable subjects in order to define RP2D, or whether an intermediate dose level or an intermittent dosing schedule will be explored in up to 6 newly enrolled subjects. Additional subjects may be added at a given dose level to further assess the safety and/or PK.

Based on above criteria, if no DLT is observed in at least 3 evaluable subjects, the SRC may decide to escalate the dose to the next cohort.

If one DLT occurs prior to a decision by the SRC to dose escalate, the cohort will be expanded to enroll 6 evaluable subjects in total. Subjects 4 to 6 may be enrolled concurrently with the first 3 subjects if complete 28-day toxicity data are not yet available for the first 3 subjects.

If 1 subject out of 6 evaluable subjects experiences a DLT, the dose will be escalated in the next cohort, unless there are other safety considerations by the SRC. The dose may also be declared the RP2D.

The number of cohorts depends on incidence of DLT. A subject may experience more than 1 DLT. Dose escalation decisions are based on the number of subjects experiencing DLT events.

Intra-subject dose escalation beyond the dose initially assigned to a subject is not permitted in Cycle 1. Those continuing to take IP beyond Cycle 1, following approval by the SRC, may have the dose level increased providing the alternative dose level has been shown to be well tolerated by at least one cohort of other subjects in this study.

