4.2. Study Endpoints

Table 2: Study Endpoints

Endpoint	Name	Description	Timeframe
Primary Phase 1	The incidence of DLTs and the incidence and severity of treatment-emergent adverse events (TEAEs)	See Section 7.6 of protocol for the definition of DLTs	Dose Escalation Phase
Primary Phase 2	Preliminary efficacy as measured by ORR	The combined incidence of CR + PR, by investigator assessment of response by RECIST 1.1	Dose Escalation and Dose expansion Phase
Secondary	Preliminary efficacy	Disease control rate (DCR), duration of response (DoR), progression free survival (PFS), overall survival (OS), and time to progression (TTP) based on investigator assessment of response using RECIST 1.1 guidelines	Dose Escalation and Dose expansion Phase
Secondary	Plasma PK parameters	Including but not limited to maximum observed concentration (C_{max}), area under the concentration time curve (AUC), time to maximum concentration (T_{max}), terminal half-life ($t_{1/2}$), apparent total body clearance (CL/F) and apparent volume of distribution (V_z/F) for CC-122 and Nivolumab after multiple dose administration	Dose Escalation Phase
[REDACTED]	[REDACTED]	[REDACTED]	[REDACTED]
[REDACTED]	[REDACTED]	[REDACTED]	[REDACTED]
[REDACTED]	[REDACTED]	[REDACTED]	[REDACTED]

Endpoint	Name	Description	Timeframe
[REDACTED]	[REDACTED]		[REDACTED]

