5. GENERAL STATISTICAL CONSIDERATIONS

5.1. Reporting Conventions

5.1.1. General Reporting Conventions

General reporting conventions for this study are:

- By default, descriptive statistics include: n (the corresponding sample size), Mean, Median, Standard Deviation, Minimum (Min), and Maximum (Max). Unless specified in the actual table shells, the mean, median, and the upper and lower limits of a 2-sided 95% confidence interval (CI) should be displayed to one more decimal place than the original data (derived analysis data). Standard deviation and standard error should be formatted to two more decimal places than the measured value. The minimum and maximum should be displayed to the same number of decimal places as the original data.
- P-values will be presented with 4 decimal places.
- Summary tables, listings, and any supportive SAS output will include a “footer” of explanatory notes that will indicate, at a minimum, the following:
 - Program and data source (e.g., SAS program, including the path that generates the output).
 - Data extraction date (e.g., the database lock date, run date). The purpose of showing the data extraction date is to link the output to a final database, either active or archived, that is write-protected for replication and future reference.
 - Output date (appearing on each output page). The output date will indicate the date the output was generated by the analysis program.
- Individual subject listings will display all data supporting corresponding tables and figures.
- If the end of treatment (EOT) visit is performed on a date different from the date of any nominal visit, the nominal visit immediately after the EOT will be used for plotting. The data from the EOT visit will not be included for any parameter mean-over-time plot.

Other general conventions include:

For the dose escalation part, subjects will be grouped according to their initially assigned dose cohort. In dose expansion part, the subjects may be categorized into different subgroups, such as HCC etiology. In addition, subjects in the same subgroup at the same dose level from both study parts will be combined for analysis as appropriate. All analyses specified in this SAP will be summarized by dose cohorts in the dose escalation part by selected subgroups in the dose expansion part, by selected subgroup at the expanded dose with subjects and by study overall in the dose expansion part, unless specified otherwise.

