11. SAFETY ANALYSIS

The purpose of this section is to define the safety parameters for the study and to summarize the safety result of the study. All summaries of safety data will be conducted using the Safety Population and will be presented by dose cohorts in the dose escalation part by selected subgroups in the dose expansion part, and by selected subgroup at the expanded dose with subjects from both parts. Safety measurements will include AEs, clinical laboratory information (including troponin-T and Brain natriuretic peptide [BNP]), vital sign measurements, 12-lead electrocardiograms (ECGs), left ventricular ejection fraction (LVEF) assessments, ophthalmological exam, and pregnancy status. Individual subject listings will be provided to support the tables.

If an EOT measurement is conducted for those subjects who discontinue from the study, the data from the EOT visit will be included as a separate visit in the summary table. In addition, the data from the EOT visit will also be included in plots for parameters of individual subjects over time.

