11.1. Adverse Events

11.1.1. Summary of Adverse Events

AEs will be analyzed in terms of treatment-emergent adverse events (TEAEs) which are defined as any AEs that start between the date of first dose of study drug and 28 days after the last dose of CC-122 or 90 days after the last dose of Nivolumab, whichever is later. All AEs will be coded using the MedDRA[®] dictionary Version 21.0 or higher.

The incidence of TEAEs will be summarized by MedDRA SOC and PT. The intensity of AEs will be graded 1 to 5 according to the National Cancer Institute (NCI) Common Terminology Criteria for Adverse Events (NCI CTCAE) Version 4.03 or higher if possible. AEs that are not defined in the NCI CTCAE Version 4.03 or higher should be evaluated for severity/intensity according to Version 3.0. For all other AEs not described in the NCI CTCAE criteria, the intensity will be assessed by the investigator as mild (grade 1), moderate (grade 2), severe (grade 3), life-threatening (grade 4) or death (grade 5).

If a subject experiences the same AE more than once with a different grade, then the event with the highest grade will be tabulated in “by grade” tables. If a subject experiences multiple AEs under the PT (SOC), then the subject will be counted only once for that PT (SOC). In addition, AEs with a missing grade will be presented in the summary table as a grade category of “Missing” and will not be imputed.

A summary table of the subject incidence rate in each of the following categories will be provided. In addition, a table for each of the following categories will be produced where the incidence rate will be tabulated by SOC and PT and provided.

- TEAEs;
- TEAEs related to CC-122, Nivolumab and study drugs (CC-122 and/or Nivolumab);
- TEAEs of NCI CTCAE grade 3 or 4 by maximum NCI CTCAE grade;

- TEAEs related to CC-122, Nivolumab and study drugs (CC-122 and/or Nivolumab) with NCI CTCAE grade 3 or 4 by maximum NCI CTCAE grade;
- Grade 5 TEAEs with death outcome;
- Grade 5 TEAEs with death outcome related to CC-122, Nivolumab and study drugs (CC-122 and/or Nivolumab);
- Serious TEAEs;
- Serious TEAEs related to CC-122, Nivolumab and study drugs (CC-122 and/or Nivolumab);
- TEAEs leading to discontinuation of CC-122, Nivolumab and both study drugs (CC-122 and Nivolumab);
- TEAEs related to CC-122 leading to discontinuation of CC-122 and both study drugs (CC-122 and Nivolumab);

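### TEAEs are tabulated only by initially assigned CC-122 cohort, so events first arising after a permitted dose increase would be charged to the lower starting dose

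*SAP*

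**What the plan says.** **Grouping.** SAP 5.1.1, on the general conventions: "For the dose escalation part, subjects will be grouped according to their initially assigned dose cohort". The same section makes cohort the default for every analysis in the SAP unless a later section says otherwise. SAP 11 does not: "All summaries of safety data will be conducted using the Safety Population and will be presented by dose cohorts in the dose escalation part".

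**Dose changes.** Protocol 7.2.1: "Intra-subject dose escalation of CC-122 is not permitted during Cycle 1, but may be permitted in later cycles if approved by the SRC". Protocol 7.8 adds a condition for subjects who continue beyond Cycle 1. With SRC approval they "may have the dose level increased providing the alternative dose level has been shown to be well tolerated by at least one cohort"; that cohort must be made up of different people.

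**Events counted.** SAP 11.1.1 defines TEAEs as "any AEs that start between the date of first dose of study drug and 28 days after the last dose of CC-122"; the window extends to day 90 after the final nivolumab infusion where that falls later. Cycles given at a raised dose therefore fall inside it. SAP 4.2 makes TEAE incidence and severity, together with DLTs, the Phase 1 primary endpoint.

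**Later-cycle toxicity.** Protocol 7.6: "Events meeting the DLT definition occurring beyond the first cycle will be taken into account when determining the RP2D".

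**Scope of the study.** SAP 15 records that the study will not enter the expansion phase. Its list of changes neither withdraws intra-subject escalation nor says how an escalated subject is to be handled.

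**The concern.** Under these rules a subject keeps the starting-dose label for as long as treatment lasts. Suppose a subject starts at one level, is raised to the next, and only then has a first Grade 3 event. The tables show that event at the starting level, and it appears nowhere against the dose being taken when it began.

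Two features make this worth a line in the SAP. First, cohorts are small, so one subject moves a percentage a long way. Second, with no expansion phase, the escalation-part tables are the trial's only tabulated evidence on toxicity by dose. A later reader who wants to know how the starting dose was tolerated would see a rate that mixes in experience from a higher dose, with nothing in the table to say so.

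**Working it through.** The plan states no figure on this point, so there is none to reproduce. The check is textual, followed by simple proportions.

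**Step 1. Does any planned output use the dose at onset?**

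- SAP 11.1.1 tabulates TEAEs by cycle of onset. That gives time, not dose.
- The tabulated lists in SAP 11.1.1 (deaths, serious events, Grade 3 or 4 events, events leading to reduction, interruption or withdrawal) are arranged by phase, cohort and subject.
- SAP 9.10 summarises CC-122 reductions and interruptions, but has no entry for increases.
- SAP 9.9 fixes the expected dose intensity by cohort. An escalated subject would show a relative dose intensity above 100%. For example, at dose level 1 (expected 10 mg/week), two cycles at 2.0 mg and four at 3.0 mg give (2 × 10 + 4 × 15) / 6 = 13.3 mg/week, or 133%. This hints at an increase but gives neither its timing nor its link to an event.
- SAP 15 sets aside the objective relating plasma concentration to safety and drops correlation analyses. The readable text of SAP 12.1.3 names only efficacy parameters.

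No described summary attributes a TEAE to the CC-122 dose being taken.

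**Step 2. Which counts are exposed?**

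- DLTs: not affected. SAP 11.1.2 confines them to Cycle 1 plus the Cycle 2 Day 1 predose assessments, and escalation within a subject is barred in Cycle 1.
- The higher cohort's column: not affected. Its numerator and denominator contain only subjects who started there.
- The lower cohort's TEAE columns: affected, for events that first arise, or first reach a higher grade, after the increase.

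**Step 3. How large can it be?** Protocol 7.8 works with cohorts of 3 or 6 evaluable subjects. Let n be the starting cohort size and k the number escalated; k is an assumption, because the documents do not give it. A subject counts once per event term, so the largest addition to the lower cohort's incidence of a given TEAE is k/n.

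| n | k | Maximum addition, k/n |
|---|---|---|
| 6 | 1 | 16.7 points |
| 6 | 2 | 33.3 points |
| 6 | 3 | 50.0 points |
| 3 | 1 | 33.3 points |
| any | 0 | 0 |

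**Step 4. A less extreme case.** Assume a true incidence r = 10% at the starting dose and a further first-onset risk q = 30% after the increase. Both are illustrative. The expected tabulated incidence is

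[(n − k) × r + k × (1 − (1 − r)(1 − q))] / n.

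With n = 6, an escalated subject's risk is 1 − 0.9 × 0.7 = 0.37:

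- k = 1: (5 × 0.10 + 0.37) / 6 = 14.5%
- k = 2: (4 × 0.10 + 0.74) / 6 = 19.0%
- k = 3: (3 × 0.10 + 1.11) / 6 = 23.5%

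All compare with 10% at the starting dose alone. With q = 20% or 40%, k = 2 gives 16.0% or 22.0%.

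**The case against.** Grouping by assigned dose is an ordinary convention and is not wrong as the main display. The effect needs an SRC-approved increase, and nothing in the documents shows that one took place. With about 20 subjects, listings and the by-cycle table let a careful reader trace late events by hand. All of this stands. It makes the point conditional and limits it to a supplementary output. It does not remove the point, because reconstruction from listings is not a prespecified summary of a primary endpoint.

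Several stronger readings are tempting, and the documents do not support them:

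- *That the RP2D decision is distorted.* A reader might infer this from Protocol 7.6. But Protocol 3.1 and 7.2.1 have the SRC decide on all available clinical, PK, pharmacodynamic and laboratory data, not on the SAP's cohort tables.
- *That the higher dose is made to look safer.* Its own column does not change. It lacks both the events and the exposure of escalated subjects, so what their inclusion would do depends on the data.
- *That most exposure and most TEAEs would follow the increase.* Two years is a maximum treatment duration, and the target level must first have been tolerated by another cohort. For one of the first three subjects at 2.0 mg, a move to 3.0 mg needs two successive 28-day windows (at least 56 days), and a move to 4.0 mg needs three (at least 84 days).
- *That the PK summaries set a precedent.* SAP 12.1.2 uses actual dose, but Protocol 6.6 samples PK only in Cycle 1, when increases are barred.
- *That the primary endpoint is defined by dose.* SAP 4.2 names TEAE incidence and severity without that qualifier; the split by dose comes from the reporting convention.

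Cutting off the cohort tables at the first raised dose is not a good remedy either. It would drop real TEAEs that SAP 11.1.1 says are to be counted.

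**Conclusion.** The point holds, conditionally. If any subject receives CC-122 above the assigned level, TEAEs that first arise there are reported only against the lower starting dose. The lower cohort's incidence can be inflated by up to 16.7 points per escalated subject in a cohort of 6, or 33.3 in a cohort of 3, and no planned summary would show it. These are ceilings: they assume that every escalated subject has a first event of the given kind after the increase. The number escalated is not in the documents, and with none the effect is zero. The damage is to the dose-safety profile as finally reported. This is an inexpensive improvement, not a flaw in the DLT analysis or a demonstrated error in dose selection.

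**What to change.** Keep the assigned-cohort TEAE tables as the main display, complete and untruncated. Add to SAP 11.1.1:

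1. The number of subjects who received CC-122 above their assigned level is reported. If there were none, a sentence says so and nothing further is needed.
2. If there was at least one, TEAEs (all, Grade 3 or higher, related, serious) are also tabulated by CC-122 dose at onset, with the number of subjects exposed and the exposure time at each dose.
3. Dose at onset is defined in advance, for example as the most recent non-zero CC-122 dose before the event began, using the start-date imputation in SAP 17.4.1.

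**Cost.** SAP wording and one extra set of tables. AE start dates and assigned and actual CC-122 doses are already needed for SAP 9.10 and 17.2, so no new data are collected and no clinical rule changes.

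**Downsides, for a footnote.** A subject can appear under more than one dose. Subjects at raised doses are selected for having tolerated earlier cycles. Delayed or cumulative toxicity is assigned to whatever dose was current. The table should be labelled supplementary and descriptive.

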5.1.2. General Definitions

General definitions for this study are:

- Where study drug or study treatment is referenced, this refers to Investigational Product (IP): CC-122 or Nivolumab, unless otherwise stated;
- The first dose date refers to the earliest dose of study drug and the last dose date refers to the latest dose of study drug.

5.2. Analysis Populations

5.2.1. Efficacy Evaluable (EE)

EE Population – All subjects who enroll, meet eligibility criteria, take at least 50% of both assigned IP in the first 2 cycles, have a baseline efficacy (tumor) assessment, and at least one post-baseline efficacy (tumor) assessment.

5.2.2. Enrolled

Enrolled Population – All subjects who are enrolled, i.e., all subjects who are assigned to study.

5.2.3. Safety

Safety Population – All subjects who enroll and take at least one dose of either IP i.e. have received at least one dose of CC-122 or Nivolumab.

5.2.4. Pharmacokinetics (PK) Evaluable

PK Evaluable Population – All subjects who enroll and receive at least one dose of either IP and have at least one measurable concentration of CC-122 or Nivolumab.

5.2.6. Reporting for Analysis Populations

In general,

- The Enrolled and Safety Populations will be used for the subject disposition.
- The demographic and baseline characteristics will be summarized on all Populations defined above.
- Drug exposure and all safety analyses (except for PK and biomarker) will be based on the Safety Population.
- Efficacy analyses (including Eastern Cooperative Oncology Group Performance Status [ECOG PS], except for PK or biomarker related endpoints) will be based on the Safety Population. Key Efficacy analyses [summary of ORR, DCR, DoR, PFS, OS and TTP] will be based on both the Safety Population and the EE Population. PK analyses will be based on the PK Population.

- 
- All listings will use the Enrolled Population unless otherwise stated.

6. SUBJECT DISPOSITION

The total number of screen failures with the reasons for failure will be summarized overall.

A summary of subject disposition will be presented by dose cohorts in dose escalation part by selected subgroups in dose expansion part, by selected subgroup at the expanded dose with subjects from both parts, and for the following analysis populations:

- Enrolled Population
- Safety Population

A tabulated summary of all analysis populations in Section 5.2 will be presented together with the subject disposition. A listing of whether a subject is excluded from those populations will be provided. A summary of subjects enrolled by site will be presented. A listing of subject enrollment (protocol version and date, informed consent date, and study phase assignment) will be provided.

Reasons for treatment discontinuation will be summarized separately for CC-122 and Nivolumab with the following categories:

- Adverse event
- Progressive disease
- Symptomatic deterioration
- Physician decision
- Withdrawal by subject
- Death
- Lost to follow-up
- Protocol violation
- Pregnancy
- Other

Reasons for discontinuation from the study will be summarized with the following categories:

- Adverse event
- Screen failure
- Withdrawal by subject
- Death
- Pregnancy
- Lost to follow-up
- Other

The following by-subject listing of subjects with demographic information attached will be provided:

- Subject listing of discontinuation
- Subject listing of screen failures
- Subject listing of visit completion
- Subject listing of previous participation

